### **Stratification Factor for Efficacy Analyses**

Baseline LDH ( $\leq$  ULN versus  $>$  ULN) will be used in all stratified analyses of the efficacy endpoints. The stratification factor value under which the subject is randomized by the IRT will be used in the efficacy analyses.

### **Dealing with Multiple Values on the Same Day**

If multiple lab values on the same day are available for a post-baseline measurement, then the value with the highest NCI CTCAE grade (or worst scenario) will be used in the assessment of shift from baseline to post-baseline. Arithmetic averages will be taken for the mean change analyses in lab values and vital signs values.

### **Definition of Baseline**

All baseline summary statistics and analyses will be based on baseline for each variable. Unless otherwise stated, baseline for a given variable will be defined as the last value for that variable obtained on or prior to the date of first dose of study drug (or randomization date for untreated subjects).

Unless otherwise specified, baseline in rest of the document refers to the Baseline defined here.

### **Definition of Final Value**

For ECOG, laboratory and vital signs variables, final value is defined as the last non-missing observation collected after the first dose of study drug in combination period to the 30 days after the last dose of study drug in combination period, or the last dose of veliparib/placebo in maintenance period if subject received any maintenance monotherapy.

Unless otherwise specified, final value in rest of the document refers to the Final Value defined here.

### **Definition of Analysis Windows**

All time points and corresponding time windows are defined for each cycle are based on Cycle Rx Day 1 of each cycle.

Visit-wise longitudinal analyses such as change from baseline to all post-baseline assessments will be performed for blood chemistry and hematology parameters, as well as urinalysis and vital sign parameters. If more than one measurement exists for a subject on a particular day, an arithmetic average will be calculated. This average will be considered to be that subject's measurement for that day.

The time windows specified in [Table 2](#) describe how the data will be assigned to the protocol specified visits. Analysis time windows are constructed using the following algorithm:

- Determine the nominal Cycle Rx Day for each scheduled visit.
- Determine the window around a specific nominal Cycle Rx Day as in [Table 2](#).
- If more than one assessment is included in a time window, the assessment closest to the nominal day should be used. If there are two observations equally distant to the nominal day, the later one will be used in analyses.

**Table 2. Time Windows for ECOG performance status**

Scheduled Visit	Nominal Cycle Rx Day	Time Window (Cycle Rx Day Range)
Baseline	Baseline	Per baseline definition
Combination Cycle X Day 1	Rx day of Combination Cycle X Day 1	[-5, 1]
Combination Cycle X Day 8*	Rx day of Combination Cycle X Day 8	[-3, +3]
Maintenance Cycle XX Day 1	Rx day of Maintenance Cycle 1 Day 1	[-5, +5]
Final Value	NA	From baseline to final value per definition

Note: X refers to 2, 3, 4 ... XX refers to 1, 2, 3, 4 ...

## 7.0 Demographic and baseline characteristics, medical history, prior oncological therapies, and concomitant medications

### 7.1 Demographic and Baseline Characteristics

Categorical demographic and baseline characteristic variables will be summarized with the number and percentage of subjects, including those with missing information. Continuous demographic and baseline variables will be summarized with summary

statistics (mean, standard deviation, median, minimum and maximum). There will be no statistical comparison for demographic and baseline characteristics.

Continuous demographic variables include age, baseline height, weight. Categorical demographic variables include gender (male, female) and race (White, Black, Asian, American Indian or Alaska Native, and Native Hawaiian or Other Pacific Islander).

Continuous baseline characteristics include baseline tumor burden (based on the sum of baseline target lesion sizes (mm)), and number of baseline lesion sites (for one subject, one site counts as one regardless of the number of lesions that it carries).

Categorical baseline characteristics include baseline LDH value ( $\leq$  ULN,  $>$  ULN), baseline ECOG performance (0, 1), medical/surgical history (yes, no), history of other cancer (yes, no), number of metastatic sites (0/1,  $\geq$  2), baseline diagnose stage M (M0, M1, unknown), tobacco use (former, current, never, unknown), and alcohol use (former, current, never, unknown).

## **7.2 Medical History**

Medical history data will be summarized and presented using System Organ Class (SOC and Preferred Terms (PT)) according to the Medical Dictionary for Regulatory Activities (MedDRA) dictionary.

The number and percentage of subjects with a particular PT will be summarized by alphabetical order of SOCs and alphabetical order of PTs within each SOC.

Subjects reporting more than one PTs within a SOC will be counted only once for that SOC. There will be no statistical comparison for medical history.

## **7.3 Prior oncological therapies, concomitant medications, and Post-Treatment Therapies**

The number and percentage of subjects who took at least one dose of concomitant medication other than study drug, and subjects who received any post treatment therapy,

will be summarized separately by the generic medication name coded by WHO dictionary.

The number and percentage of subjects who have prior oncological therapies will be summarized by generic medication name and treatment setting (adjuvant, neo-adjuvant, metastatic). In addition, the best response of any therapies prior to study drug (or randomization for non-treated subjects) will be summarized.

There will be no statistical comparison for prior oncological therapies and other medications.

## **8.0 Subjects Disposition**

Analyses for the subject disposition will be performed on ITT population. The screen failure reasons will be summarized for the screen failure subjects separately. The number and percentage of subjects will be summarized overall, by treatment arm, and by country for each of the following categories:

- Subjects who screen failed
- Subjects who were randomized into the study
- Subjects who never received any study drug
- Subjects who received randomized study drug
- Subjects who received study drug other than randomized
- Subjects who were in maintenance phase
- Subjects who discontinued study drug due to all reasons and primary reason
- Subjects who discontinued carboplatin due to all reasons and primary reason
- Subjects who discontinued etoposide due to all reasons and primary reason
- Subjects who discontinued maintenance veliparib/placebo due to all reasons and primary reason
- Subjects who discontinued study due to all reasons and primary reason

## 9.0 Study Drug Exposure

Analyses for the study drug exposure will be performed on AST population. Some definitions are provided as follows.

1. Combination therapy period

The following calculations only include data prior to maintenance monotherapy.

- a. Total number of cycles a certain subject exposed to veliparib/placebo: total number of cycles during which subject received at least one dose of veliparib/placebo.
- b. Duration of veliparib/placebo of a certain subject: last dose date of veliparib/placebo of this subject minus the first dose date of veliparib/placebo of this subject plus 1.
- c. Total number of days a certain subject exposed to veliparib/placebo overall, and by cycle, respectively: total number of days this subject received veliparib/placebo (excluding days not on study drug) overall, and by cycle, respectively.
- d. Average daily dose of veliparib/placebo of a certain subject overall, and by cycle, respectively: total administered dose of veliparib/placebo of this subject divided by total number of days this subject exposed to veliparib/placebo overall, and by cycle, respectively.
- e. Dose intensity (DI) of veliparib/placebo of a certain subject is defined as the ratio of ATD (actual total dose) of veliparib/placebo of this subject and PTD (planned total dose) of veliparib/placebo of this subject, expressed as a percentage (%). ATD and PTD of veliparib/placebo will be defined in [Table 3](#).

For carboplatin and etoposide, analysis of DI will be performed. Dose intensity (DI) of carboplatin/etoposide of a certain subject is defined as ratio of ATD of carboplatin/etoposide of this subject and PTD of carboplatin/etoposide of this subject,

expressed as a percentage (%). ATD and PTD of carboplatin/etoposide will be defined in [Table 3](#).

Descriptive statistics (mean, standard deviation, median, and range) will be used to summarize total number of cycles, duration, and total number of days, average daily dose, and DI of veliparib/placebo in combination phase, and DI of carboplatin/etoposide in combination phase. The actual total dose (ATD), planned total dose (PTD), and dose intensity (DI) for veliparib/placebo, carboplatin and etoposide prior to maintenance monotherapy period are presented in [Table 3](#).

**Table 3. Definition of Actual Total Dose, Planned Total Dose, And Dose Intensity for Study Drugs Prior To Maintenance Period**

	ATD (Actual Total Dose)	PTD (Planned Total Dose)	DI (Dose Intensity)
Veliparib/placebo	Actual total dose (mg)	480 mg* 14* (actual number of veliparib/placebo combination cycles –1) +480 mg* actual veliparib/placebo dosed days in the last combination cycle	100*ATD/PTD
Carboplatin	Actual total AUC (mg/mL/min)	5 mg/mL/min* actual number of chemo cycles	100*ATD/PTD
Etoposide	Actual total dose (mg/m  )	3*100 mg/m  * actual number of chemo cycles	100*ATD/PTD

Actual number of veliparib/placebo combination cycles refers to the number of cycles subjects are exposed to veliparib/placebo prior to the initiation of maintenance therapy (if any) as captured on drug administration pages in EDC.

Actual total dose of veliparib/placebo in combination cycles is calculated excluding premature veliparib/placebo doses, that being said, we exclude any veliparib/placebo dose that was administered 2 days (not necessarily continuous doses) before the start date of

carboplatin or etoposide in that cycle, whichever occurs first. If a subject received no carboplatin and etoposide in a cycle, which indicates a protocol deviation, then veliparib/placebo administered in this cycle will be excluded.

Actual number of chemo cycles refers to the number of cycles subjects exposed to carboplatin/etoposide as captured on drug administration pages in EDC.

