### **5.5 Treatments**

#### **5.5.1 Treatments Administered**

Phase 1 subjects will receive the following:

- Designated doses of veliparib BID on Days –2 through 5 or Day –2 through 12 (14-day schedule) or Day –2 to 19 (continuous schedule) + Carboplatin AUC

5 mg/mL\*min administered on Day 1 and Etoposide 100 mg/m^2 administered on Days 1 through 3 of each 21-day cycle for up to 4 cycles.

- Exception: Phase 1 subjects receiving non-continuous veliparib will have their Cycle 2 dosing schedule altered as follows to allow for the evaluation of veliparib effect on etoposide exposure: veliparib BID on Days 2 through 5 or Days 2 through 12 + Carboplatin AUC 5 mg/mL\*min administered on Day 1 and Etoposide 100 mg/m^2 administered on Days 1 through 3 of a 21-day cycle.
- Phase 1 subjects with SD, PR or CR at the completion of all scheduled combination therapy cycles will receive veliparib (400 mg) monotherapy, BID continuously in 21-day cycles starting on Day 1 of each cycle starting at Cycle 5.

Phase 2 subjects will receive the following:

- Veliparib/Placebo 240 mg BID on Day -2 through 12 (14-day schedule) + Carboplatin AUC 5 mg/mL\*min administered on Day 1 and Etoposide 100 mg/m^2 administered on Days 1 through 3 of each 21-day cycle for up to 6 cycles.
- Phase 2 subjects with SD, PR or CR at the completion of combination therapy cycles will receive veliparib (400 mg) or placebo monotherapy, BID continuously in 21-day cycles starting on Maintenance Day 1 of each cycle.

The sequence of administration is as follows on days when veliparib is dosed in combination with chemotherapy as described in [Figure 3](#):

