## 3. Dose reduction, delay, and interruption,

The numbers and percentages of subjects having dose reduction or interruption or delay for each study drug will be summarized for each treatment arm prior to maintenance monotherapy period. If a subject has any dose reduction from the previous dose of a certain drug, this subject will be considered as having experienced dose reduction of this drug. If the difference between the first dose dates of two adjacent cycles of a certain

drug is more than 21 days, the subject will be considered as having experienced a dose delay of this drug. If a subject skips one or more consecutive dosing days of any drug within a cycle, then this subject is considered as having dose interruption of this drug.

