#### **14.1.3.1 Safety Monitoring Guidelines**

The following safety data recorded in the clinical trial database will be reviewed overall and between treatment arms:

- Subject disposition;
- Dose intensity and dose reduction/interruption summary for study drug (veliparib);
- Treatment-emergent adverse events (AEs);
- AEs/SAEs relationship to study drug (veliparib);
- Treatment-emergent serious adverse events (SAEs);
- AEs leading to dose reduction/interruption of study drug (veliparib);
- Discontinuation of study drug (veliparib) due to AEs not related to disease progression;
- AEs leading to dose reduction/interruption of chemotherapy;
- Rates of death; and
- Laboratory data.

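### SAP Table 3 does not measure delivery of the planned veliparib dose in the combination period: last-cycle shortfalls drop out, and two exclusion rules put actual and planned dose out of step

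*SAP*

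**What the plan says.** The Phase 2 schedule in Protocol Section 5.5.1 is "Veliparib/Placebo 240 mg BID on Day -2 through 12 (14-day schedule"), that is, Days -2, -1 and 1 to 12. SAP Table 1 gives the same days.

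SAP Section 9.0 defines DI as 100 × ATD/PTD, actual over planned total dose. For veliparib/placebo before maintenance, Table 3 builds PTD from two terms. The first is "480 mg* 14* (actual number of veliparib/placebo combination cycles –1"). The second is 480 mg times the "actual veliparib/placebo dosed days in the last combination cycle". The cycle count is defined as "the number of cycles subjects are exposed to veliparib/placebo prior to the initiation of maintenance therapy (if any"), so it counts cycles taken, not cycles planned.

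The other rows work differently. Carboplatin PTD is AUC 5 times the chemotherapy cycles received. Etoposide PTD is 3 × 100 mg/m² times the same count. Neither makes an exception for the last cycle. In Table 4, maintenance PTD is 800 mg times calendar duration, so days skipped between start and end do count against DI.

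The text under Table 3 adjusts ATD only. Its stated aim is to leave out *premature* veliparib. Its rule is that "we exclude any veliparib/placebo dose that was administered 2 days (not necessarily continuous doses) before the start date of" chemotherapy, taking the earlier of the two drugs within each cycle. If a cycle contains neither chemotherapy drug, "then veliparib/placebo administered in this cycle will be excluded". No matching adjustment to PTD is given.

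**The concern.** A planned dose should come from the plan. For the last combination cycle the veliparib denominator follows what the subject took, so a shortfall of whole days there cannot appear. Every subject has a last cycle, so this is not confined to those who stop early. The two ATD exclusions then remove doses from the numerator that the denominator still expects.

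DI is the only summary in Section 9.0 that sets veliparib delivery against the plan. Average daily dose is computed over dosed days, and the cycle and day counts have no planned total beside them. As written, the veliparib figure would appear in the same report as the chemotherapy figures without being comparable to them.

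**Working it through.** **1. The plan's own figure.** Days -2, -1 and 1 to 12 are 14 dosing days. 2 × 240 mg × 14 = 6,720 mg per cycle, which equals Table 3's 480 × 14. The per-cycle plan is right; the problem is where it is not applied.

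**2. The last-cycle term.** DI = 100 × ATD/PTD. At full dose the 480 mg cancels, so days can be used. The Day -2 dose is counted here.

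| Subject on full dose | Table 3 | 14 days for each started cycle |
|---|---|---|
| Three full cycles, then 5 days of Cycle 4 | 47/(42 + 5) = 100% | 47/56 = 83.9% |
| Stops after 5 days of Cycle 1 | 5/5 = 100% | 5/14 = 35.7% |
| Full Cycle 1, stops after 7 days of Cycle 2 | 21/21 = 100% | 21/28 = 75.0% |
| Four cycles, 7 days missed in Cycle 2 | 49/56 = 87.5% | 49/56 = 87.5% |
| Four cycles, 7 days missed in Cycle 4 | 49/49 = 100% | 49/56 = 87.5% |

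The last two subjects took the same amount of drug and score differently only because of which cycle the gap fell in.

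Comparison with the chemotherapy rows: a subject stops everything after Day 1 of Cycle 4. Etoposide DI is (9 + 1)/12 = 83.3%. Veliparib DI is 45/45 = 100%, although only 3 of that cycle's 14 days were taken.

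**3. Where the result is not 100%.** Dose reductions and earlier missed days still lower DI.
- Full Cycle 1, then 200 mg BID with a stop after 7 days of Cycle 2: (6,720 + 2,800)/(6,720 + 3,360) = 94.4%. Completing Cycle 2 at that dose would give (6,720 + 5,600)/13,440 = 91.7%, so stopping raises DI.
- Four days missed in Cycle 1, then a stop after 7 days of Cycle 2: (10 + 7)/(14 + 7) = 81.0%. Completing Cycle 2 would give 24/28 = 85.7%. The difference is only a change in the weight of Cycle 1; the 7 lost days themselves are not charged. On 14 days per started cycle it is 17/28 = 60.7%.

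**4. The Day -2 exclusion, read literally.** Day -2 is exactly 2 days before Day 1. Removing it from ATD while PTD keeps 14 days gives a fully adherent subject 13/14 = 92.9%. If *2 days* is read as both pre-chemotherapy days, it is 12/14 = 85.7%. On the Day -2 reading, with PTD unchanged, the first subject in the table scores 43/47 = 91.5%, not 100%. The two defects therefore push in opposite directions, and their sizes cannot be quoted together as if they came from one reading.

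**5. A cycle without chemotherapy.** Four full cycles, then two veliparib days in a fifth cycle with no chemotherapy: ATD = 56 days, PTD = 14 × 4 + 2 = 58 days, DI = 96.6%.

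**6. After the change set out under fix.** Full adherence scores 100%. The first subject in the table scores 83.9%. The subject in step 5 scores 56/56 = 100%.

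**The case against.** The best defence is that DI here is an on-treatment measure: every row uses cycles or duration actually received, and such a measure is usable if labelled. That stands in part, because the chemotherapy rows also ignore cycles never started. But those rows still charge the full plan to the last cycle received, and the maintenance row charges skipped days. Only the combination veliparib row follows the days taken, so the convention does not explain it.

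On Day -2, the defence is strong. The word *premature*, the 14 days in PTD, and Protocol Section 5.7.2.1, which has Days -2 and -1 repeated when toxicity holds up chemotherapy, all point to doses more than 2 days ahead. This is an ambiguous rule, not proof that the dose was dropped. The wording still matters, because SAP Section 3.0 says the document is there to guide programming. A chemotherapy-free cycle is, by the SAP's own text, a protocol deviation, so few subjects should be affected.

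A reader might infer that early stopping is hidden altogether. It is not. Section 8.0 tabulates discontinuations with reasons by arm; Section 9.0 summarizes cycles, duration and days, and counts subjects with interruptions; Section 11.2 tabulates adverse events leading to discontinuation.

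A reader might also fault the rule that if the gap between first doses of adjacent cycles of a "drug is more than 21 days, the subject will be considered as having experienced a dose delay of this drug", since Protocol Section 5.3.1.1 allows about ±1 day around infusion days. But that window concerns study procedures, and the SAP rule compares first-dose dates for each drug. A 21-day limit follows the cycle length and applies to all arms, and a 23-day limit would miss real delays of one or two days. That choice is a preference.

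**Conclusion.** The point holds for the definition. Table 3 does not measure delivery of the planned veliparib dose in the combination period. For a subject on full dose, days missed or lost in the last cycle leave DI at 100%, against 84% in the worked example; this assumes the Day -2 dose is counted. Read literally, the exclusion rule instead gives 93% for full adherence. The chemotherapy-free rule gives 97% where all planned doses in cycles with chemotherapy were taken.

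Three stronger conclusions are not supported. The documents contain no DI results and no programs, so it cannot be said that reported figures are wrong. It is not true that every early stopper scores 100%; that needs full dosing with no earlier reductions or missed days. And although the DMC list in SAP Section 14.1.3.1 includes "Dose intensity and dose reduction/interruption summary for study drug (veliparib"), SAP Section 4.4 records one review, on 18 October 2017, with no further review needed before database lock. This SAP is dated 15 November 2018, so its definition cannot have governed what the DMC saw.

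The consequence is limited to a descriptive exposure summary in the final report. No efficacy conclusion depends on it.

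**What to change.** In SAP Section 9.0:
- Set veliparib/placebo PTD in Table 3 to 480 mg × 14 × number of combination cycles started, in line with the chemotherapy rows.
- Word the ATD exclusion as doses given *more than 2 days before* the first chemotherapy dose of that cycle.
- Where a cycle has no chemotherapy, drop it from both ATD and PTD.
- Label DI as relative to cycles started. Cycles never started are still not counted: a subject who stops after one full cycle scores 100% under the new rule too, so DI should be read beside the number of cycles and the discontinuation table.

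The cost is a few lines of text and minor reprogramming. With Day -2 counted, DI will come out somewhat lower, including for subjects who stop mid-cycle because of progression rather than intolerance. A footnote to the table should say so.

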## 5.7 Dose Reductions or Delays

If a subject experiences an adverse event that results in a delay in starting a cycle or requires that study regimen is delayed or interrupted during a cycle, the subject will complete the planned activities per Section 5.7.1 until resuming treatment.

Study drug interruptions for events that are clearly not related to the study drug treatment, (e.g., underlying cancer, planned surgical procedures or acute viral illnesses), should not necessitate a dose reduction. The timing of dose resumption should be at the discretion of the Investigator. Study treatment may be delayed for up to 21 days due to toxicity. Toxicity-related delays greater than 21 days will result in study treatment discontinuation.

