#### **Neutropenia or Febrile Neutropenia**

For febrile neutropenia with absolute neutrophil count (ANC)  $< 500/\text{mm}^3$  and a single temperature of  $> 38.3^\circ\text{C}$  ( $101^\circ\text{F}$ ) or a sustained temperature of  $\geq 38^\circ\text{C}$  ( $100.4^\circ\text{F}$ ) for more than one hour, requiring intravenous antibiotics:

- a. Doses of both carboplatin and etoposide drugs should be reduced to the next lower dose level for all subsequent cycles of chemotherapy. Suggested dose reduction levels are outlined in [Table 14](#).
- b. Implement dose reductions, as outlined in [Table 19](#).
- c. Initiate prophylactic neutrophil growth factors (e.g., G-CSF) after the first episode and in accordance with local SOC practices, ASCO or NCCN guidelines.
- d. If ANC counts do not recover within 3 weeks, discontinue all protocol therapy.

For treatment delays of more than 7 days due to neutropenia, carboplatin and etoposide should be dose-reduced to next lower dose level for all subsequent cycles of chemotherapy, as outlined in [Table 19](#).

For nadir neutropenia in the absence of fever or with fever that is successfully treated by oral antibiotics, there will be no dose adjustment.

ANC must be  $\geq 1,500/\text{mm}^3$  on Day 1 of each cycle (mandatory). If the ANC is lower than  $1,500/\text{mm}^3$ , then dosing of all drugs (carboplatin, etoposide and veliparib) will be delayed until recovery to the required ANC.

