## 2. Maintenance monotherapy period

Duration, total number of days, average daily dose, and DI of veliparib/placebo as described above will be summarized by descriptive statistics for veliparib/placebo in maintenance monotherapy.

The actual total dose (ATD), planned total dose (PTD), and dose intensity (DI) for veliparib/placebo in the maintenance monotherapy period is presented in the [Table 4](#).

**Table 4. Definition of Actual Total Dose, Planned Total Dose, And Dose Intensity for Veliparib/Placebo in Maintenance Period**

	ATD (Actual Total Dose)	PTD (Planned Total Dose)	DI (Dose Intensity)
veliparib/placebo	Actual total dose (mg)	800 mg* duration of maintenance therapies	100*ATD/PTD

Duration of maintenance therapy is calculated by subtracting the start date of maintenance therapy from the end date of maintenance therapy plus 1.

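### SAP Table 3 dose intensity for carboplatin and etoposide has no time term, so a cycle delayed without dose reduction still scores 100% and no planned output measures chemotherapy dose per unit time

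*SAP*

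**What the plan says.** SAP 9.0, item 1 states the measure for the combination period: "Dose intensity (DI) of carboplatin/etoposide of a certain subject is defined as ratio of ATD of carboplatin/etoposide of this subject and PTD", as a percentage. In Table 3 the planned total for carboplatin is "5 mg/mL/min* actual number of chemo cycles". For etoposide it is three daily doses of 100 mg/m² times the same cycle count. The count is of cycles given: "Actual number of chemo cycles refers to the number of cycles subjects exposed to carboplatin/etoposide as captured on drug administration pages in EDC".

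Table 4, for maintenance veliparib/placebo, has a different kind of denominator: "800 mg* duration of maintenance therapies".

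Delay is handled separately in SAP 9.0, item 3: "The numbers and percentages of subjects having dose reduction or interruption or delay for each study drug will be summarized for each treatment arm". The trigger is the gap between first-dose dates of adjacent cycles. If that gap for a given "drug is more than 21 days, the subject will be considered as having experienced a dose delay of this drug". SAP 11.2 adds a count of subjects whose adverse events led to reduction, interruption or delay of any of the drugs, with several actions from one event counted once.

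Protocol 5.7 allows substantial delay: "Study treatment may be delayed for up to 21 days due to toxicity". Under Protocol 5.7.2.1.1, if the ANC on Day 1 is too low, dosing of all drugs "will be delayed until recovery to the required ANC".

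**The concern.** Dose intensity normally means dose per unit time. Here it measures only reduction or omission within the cycles given. In a placebo-controlled add-on trial, a natural exposure question is whether veliparib impairs delivery of the chemotherapy backbone. Protocol 3.7 expects veliparib toxicity to overlap with that of carboplatin/etoposide in myelosuppression and nausea/vomiting.

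Cycle delay is one route by which such toxicity could reduce chemotherapy delivery, and the Protocol's own rules can produce it at full dose:

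- neutropenia delays of 7 days or less, which carry no suggested reduction (5.7.2.1.1, Table 19);
- Day 1 platelet holds without a Grade 4 nadir (5.7.2.1.1, Table 19);
- holds for nausea or vomiting, where carboplatin and etoposide doses are not to be modified (5.7.2.1.2);
- cycles postponed because veliparib/placebo cannot yet be restarted (5.7.1, combination therapy, item 5).

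In each case DI stays at 100% while dose per week falls. An arm comparison of DI would then miss a difference in chemotherapy density that could bear on the reading of the PFS result.

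**Working it through.** **Inputs.** From SAP Table 3: AUC 5 per cycle; etoposide 3 × 100 = 300 mg/m² per cycle; DI = 100 × ATD/PTD. From the Protocol: 21-day cycles, 4 to 6 combination cycles, toxicity delay up to 21 days. Table 16 lists the reduction levels (carboplatin AUC 4; etoposide 75, then 55 mg/m²). The documents give no expected delay lengths or frequencies, so the delays below are assumptions spanning the permitted range. The plan states no DI figure to reproduce.

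**Formulas.** For n cycles with D total delay days:

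- Table 3 DI = dose given / (per-cycle dose × n). D does not appear.
- Time-based value = (dose given / (21n + D)) / (per-cycle dose / 21) = DI × 21n / (21n + D).

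**Full dose, every later cycle delayed by d days, so D = (n − 1)d:**

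| d (days) | Table 3 DI | Time-based, n = 4 | Time-based, n = 6 |
|---|---|---|---|
| 3 | 100% | 84/93 = 90.3% | 126/141 = 89.4% |
| 7 | 100% | 84/105 = 80.0% | 126/161 = 78.3% |
| 14 | 100% | 84/126 = 66.7% | 126/196 = 64.3% |
| 21 | 100% | 84/147 = 57.1% | 126/231 = 54.5% |

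The 14- and 21-day rows apply only if no reduction follows, for example after platelet holds.

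**With the suggested reductions after neutropenia delays of more than 7 days, n = 4:**

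- One 14-day delay before Cycle 2, first reduction level afterwards. Carboplatin DI = (5 + 4 + 4 + 4)/20 = 85.0%; time-based 85.0% × 84/98 = 72.9%. Etoposide DI = (300 + 3 × 225)/1200 = 81.25%; time-based 69.6%.
- All three intervals delayed 14 days, with etoposide reduced again after the second episode. Carboplatin DI 85.0%; time-based 85.0% × 84/126 = 56.7%. Etoposide DI = (300 + 225 + 165 + 165)/1200 = 71.25%; time-based 47.5%.

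DI registers the reductions, but it exceeds the time-based value whenever D > 0.

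**Arm level (assumed rates).** Suppose 40% of intervals in Arms A and B and 20% in Arm C are 7 days late, at full dose, over four cycles. Mean elapsed time is 84 + 21 × 0.4 = 92.4 days against 84 + 21 × 0.2 = 88.2 days. Delivery per week at those means is 84/92.4 = 90.9% against 84/88.2 = 95.2%. DI is 100% in every arm.

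**Early stopping.** Two on-time, full-dose cycles give Table 3 DI = 10/10 = 100%. The time-based ratio is also 100%, because both dose and elapsed time stop at Cycle 2. Against four planned cycles, the dose is 10/20 = 50%.

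**The case against.** The best counter-argument is that delays are already reported elsewhere, and much of it stands. Under the arm-level rates above, and with independent intervals, the item 3 table would show 1 − 0.6³ = 78.4% of subjects in Arms A and B with a delay, against 1 − 0.8³ = 48.8% in Arm C. That imbalance would be plain to see. SAP 11.2 also covers adverse events leading to delay. The combination-period duration of veliparib/placebo in SAP 9.0, item 1 stretches with delay too: four on-time cycles span 3 × 21 + 14 = 77 days, against 98 days with 7-day delays. So although a reader might infer that delays are hidden and that the report could credibly call chemotherapy delivery unaffected, the documents do not support this.

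None of these outputs gives the missing quantity, however. The item 3 flag treats a 22-day and a 42-day interval alike and ignores repeats. The 11.2 count pools three actions across the drugs. Veliparib/placebo duration mixes the number of cycles with delay, and chemotherapy may continue after veliparib stops (Protocol 5.4.1.1).

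Two other stronger readings also fail. A reader might infer that delay is the main way marrow toxicity would weaken chemotherapy. The documents give no frequencies, and they set out dose reduction as a parallel route, which DI captures. A reader might also infer that DI stays at 100% after any delay. Where the suggested reductions after neutropenia delays of more than 7 days are applied, it does not. Those reductions are only suggestions, for use where no local label, standard of care or SmPC is available (Protocol 5.7.2.1), so full-dose delay beyond 7 days remains possible too.

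Finally, the formula is stated openly and DI is descriptive. That limits the severity of the point but does not answer it.

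**Conclusion.** The point holds as a minor one. Carboplatin and etoposide DI contains no time, unlike maintenance DI under the same name, and it overstates delivery per unit time whenever cycles are late. The firmest illustration is 100% against 80% for four full-dose cycles each 7 days late (six cycles: 78%), because a delay of that length triggers no suggested reduction. The 14- and 21-day full-dose figures are upper bounds conditional on no reduction. With reductions, the examples show carboplatin DI of 85.0% against 72.9% or 56.7%. The arm-level gap of about 91% against 95% rests on assumed delay rates. Delays are unquantified in the planned outputs, not concealed. No efficacy endpoint, test, alpha or sample size depends on this measure.

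**What to change.** In SAP 9.0:

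1. Add, for carboplatin and etoposide separately and by arm, a relative dose intensity per week: [ATD / ((first-dose date of last chemotherapy cycle − first-dose date of Cycle 1 + 21)/7)] divided by [planned per-cycle dose / 3 weeks]. For four full-dose cycles each 7 days late, carboplatin gives (20/15)/(5/3) = 80%.
2. Keep the present ratio, but rename it 'percent of planned dose in cycles given'.
3. Summarise the number of chemotherapy cycles and the cumulative delay days by arm, because both ratios return 100% for a subject who stops early after on-time, full-dose cycles.

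The cost is SAP wording and a few derived variables. Item 3 already relies on the same first-dose dates, and Protocol 5.5.8 has carboplatin and etoposide doses recorded on the eCRF. The downside is a somewhat less favourable descriptive figure if delays occur.
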